1.0 INTRODUCTION

The outcome of acute myeloid leukemia (AML) and myelodysplastic syndrome (MDS) in patients ≥ 55 years still remains unsatisfactory, with a low complete remission (CR) rate and poor overall survival (OS) due to a variety of reasons including increased incidence of poor-risk cytogenetics, increased activation of RAS, Src, and TNF pathways and intrinsic resistance of leukemic blasts to therapeutic agents. The 30-day induction mortality is also high and ranges from 10-50% and this is due to prolonged pancytopenia, febrile neutropenia and other systemic side effects that burden the already aging patient with comorbidities. [1-3]. Allogeneic stem cell transplantation (alloSCT) has curative potential; however, it is associated with severe graft-versus-host disease (GVHD), infections, and other treatment related morbidities or mortality for a high proportion of elderly patients [4, 5]. Thus, recent work has centered on less toxic ways to manipulate donor cells to achieve antitumor benefits.

A pilot study performed in China in elderly patients with AML treated with conventional chemotherapy followed by infusion of human leukocyte antigen (HLA) mismatched G-CSF mobilized peripheral blood stem cell infusion (G-PBSC) reported higher CR and disease-free-survival (DFS) rates, faster neutrophil and platelet recovery, and no GVHD or increase in treatment-related mortality [6]. Interestingly, although no patients exhibited full or mixed chimerism, donor microchimerism was monitored and observed in all four women who had male donors (sons or brothers). This may be due to long-term maternal-fetal microchimerism, and studies of HLA-haploididentical allo-SCT have shown improved outcomes after transplantation from noninherited maternal antigen (NIMA) mismatched donors [7]. Improved responses after HLA-mismatched G-PBSC infusion may also be due to natural killer (NK) cells: infusion of haploididentical NK cells from killer immunoglobulin-like receptor (KIR) ligand mismatched donors have shown alloreactivity against leukemia [8, 9]. Because induction and consolidation chemotherapy followed by infusion of HLA-haploididentical cells, or donor lymphocyte infusion (DLI), is a new procedure, our first priority is to replicate the above study as a Phase I trial to assess safety.

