3.7 Infusion of HLA-mismatched peripheral blood stem cells in elderly AML

A recent Chinese study reported that mice infused with a high dose of G-CSF–mobilized allogeneic spleen cells ($3-12 \times 10^7$) after cytarabine chemotherapy exhibited rapid hematopoietic recovery and persistent microchimerism without GVHD despite absence of GVHD prophylaxis and immunosuppressive treatment [6]. On the basis of these observations, they designed a clinical control study to investigate the effects of G-PBSC combined with conventional induction and intensive postremission chemotherapy on outcomes of AML in elderly patients. Fifty-eight AML patients aged 60-88 years were randomly assigned to receive induction chemotherapy with cytarabine and mitoxantrone (control group; n=28) or same chemotherapy plus HLA-mismatched G-PBSCs (G-PBSC group; n=30) (median CD3+ cell dose: 0.9×10^{10} CD3+ cells/kg recipient body weight). Patients who achieved CR received another 2 cycles of postremission therapy with intermediate-dose cytarabine plus G-PBSCs. The complete remission rate was significantly higher in the G-PBSC group than in the control group (80.0% vs. 42.8%; $P = .006$). The median recovery times of neutrophils and platelets in the G-PBSC group were 11 days and 14.5 days, respectively, and 16 days and 20 days in the control group. The 2 year probability of disease-free survival was significantly higher in the G-PBSC group than in the control group (38.9% vs. 10.0%; $P = .01$). No graft-versus-host disease was observed in any patient.

Given that none of these patients experience engraftment, yet there was a significant improvement in disease free survival, we hypothesize that these results were due to infused donor lymphocytes rather than CD34+ stem cells. As a result, G-PBSC may not be necessary and HLA-haploidentical DLI would suffice.

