11.0 STUDY DESIGN AND ANALYSIS

11.1 Primary Objectives:

10.1.1 Safety: Evaluate the safety of HLA-haploidentical DLI combined with conventional induction and consolidation chemotherapy in terms of unacceptable toxicity as defined in section 7.0.

A maximum of 30 subjects will be consented for a maximum of 21 evaluable subjects accrued to this protocol over a period of 2 years. Safety will be evaluated by the number of subjects with unacceptable toxicity as defined by any of the following:

- i. Grade III or IV aGVHD of the gut or liver or Grade IV aGVHD of the skin lasting > 7 days;
- ii. Grade IV CTCAE toxicity attributable to DLI (e.g. infusion reaction, as opposed to Grade IV CTCAE toxicity from chemotherapy) and lasting >7 days
- iii. Treatment-related mortality (TRM), keeping in mind that anticipated mortality from standard induction chemotherapy in the elderly ranges from 11% for subjects 55-65 years-old with ECOG 0 to 50% for subjects older than 75 years with ECOG 2 [1].

Simon's optimal two stage design will be applied. These rules permit the study to be closed early if there is evidence that the true unacceptable toxicity rate is ≥ 0.40 . The stopping rules in the table below will also allow us to test the null hypothesis that the true toxicity rate is ≥ 0.40 against the alternative hypothesis that the true toxicity rate is ≤ 0.20 . The Type I and II error rates for this design are 0.15 and 0.2, respectively. Given that the true toxicity rate is 0.40 (0.20), the probability of stopping the trial at Stage 1 to accept the null hypothesis is 0.7 (0.16). The significance level of this design is 0.15 and the power is 0.80.

| Stage | Total Accrual | Close study/therapy if number of subjects with unacceptable toxicity is \geq |
|-------|---------------|--|
| 1 | 11 | 4 (45%) |
| 2 | 21 | 7 (33%) |

Rates of unacceptable toxicity will be calculated and monitored with the stopping rules in the table above. Toxicity in the other categories will be informally monitored and tabulated by Type and Grade, but they will not be used to determine tolerability of the procedure.

Chemo with Adoptive Haplo DLI

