11.2.3 Evaluate efficacy with respect to disease response and survival.

Additional efficacy endpoints include response rate, DFS, EFS, and OS. The response rate will be calculated with one sided 85%

Chemo with Adoptive Haplo DLI

confidence interval. DFS, EFS, and OS will be estimated using the method of Kaplan and Meier.

11.2.4 Evaluate immune recovery.

Immune reconstitution results will be tabulated and recorded. For the evaluation of recovery of immune function post-engraftment, we will use descriptive statistics of cytokine profiles, lymphocyte and NK enumeration and flow-based assays and make patient-specific plots of immune function parameters across time. These measurements will be performed prior to induction, prior to each round of consolidation, 8 weeks after the last cycle of consolidation, and every 3 months after treatment for up to 2 years. Specifically, we will:

1. monitor leukocyte subsets using flow cytometry:
 - CD3+
 - CD4+
 - CD8+
 - regulatory (CD4+, CD25+, CD62L+)
 - cytotoxic/late memory (CD8+, CD57+, CD28-) and activated (CD8+, HLADR+) T cells
 - naïve CD4+ T cells with L-selectin expression (CD4+, CD45RA+/CD45RO-, CD62L+)
 - gamma-delta T cells
 - B cells (CD19+, CD3-, CD16-, CD56-)
 - natural killer cells (NK) (CD3-, CD16+/CD56+, CD107+)
 - natural killer T cells (NKT) (CD3+, CD16+/CD56+, CD107+),
 - plasmacytoid dendritic cells (DCs) (CD123+, CD11c-)
 - myeloid DCs (CD123-, CD11c+)
2. quantify recent thymic immigrants by the presence of TCR rearrangement excision circles (TREC) performed by real-time quantitative-PCR of DNA collected from an isolated fraction of CD31 T cells
3. perform next generation sequencing of TCR gene rearrangements to analyze diversity in the TCR repertoires produced by the rearrangements of the variable region genes.
4. in vitro assays of NK function (measure CD16 expression, intracellular CD107a degranulation and cytokine secretions of IFN γ and TNF α after 4 hour co-culture with an effector:target ratio of 2:1)
5. measure immunoglobulin levels as a function of B-cell activity and recovery

Chemo with Adoptive Haplo DLI

6. measure cytokine levels, particularly IL1, IL1-beta, IL2, IL6, IL8, IL15, IL21, IFN-gamma, TNF-alpha, TGF-beta, CRP
7. microchimerism monitoring to determine the level of donor cells (as well as the presence of any pre-existing maternal-fetal microchimerism)
8. KIR typing to determine the effect of KIR ligand mismatch
9. PD1/PDL1/PDL2 expression (marker of T cell exhaustion)

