11.2.5 Evaluate hematopoietic recovery.

Time to neutrophil and platelet recovery will be reported using descriptive statistics. Time to neutrophil recovery is defined according to the Center for International Blood and Marrow Transplant Research (CIBMTR) reporting guidelines. This is defined as the date of the first of three consecutive laboratory values where the ANC $\geq 500/\mu\text{l}$. If daily laboratory values were not obtained, ANC recovery is defined as three consecutive laboratory values drawn more than a day apart as long as the ANC remains $\geq 500/\mu\text{l}$. The CIBMTR defines the time to platelet recovery as the date of the first of three consecutive laboratory values obtained on different days where the platelet count was $> 20,000/\mu\text{l}$ without transfusion.

11.3 Subgroup analysis:

Subgroup analysis will be conducted based on age (55-70 vs >70), sex, WHO classification, relationship between donor and recipient, pre-existing maternal-fetal microchimerism in mother-child pairs, presence of post-infusion donor chimerism and microchimerism, HLA mismatch, and KIR-ligand mismatch.

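### Time to neutrophil and platelet recovery is to be summarised descriptively, with no rule for subjects who die or start re-induction before they recover

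*Combined protocol and SAP*

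**What the plan says.** Hematopoietic recovery is a secondary objective (Section 2.2.5), and count recovery is also listed among the additional efficacy endpoints in Section 11.1.2. The analysis in Section 11.2.5 is one sentence: "Time to neutrophil and platelet recovery will be reported using descriptive statistics".

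The rest of that section defines the event. For neutrophils, "This is defined as the date of the first of three consecutive laboratory values where the ANC" reaches the threshold. For platelets, "The CIBMTR defines the time to platelet recovery as the date of the first of three consecutive laboratory values obtained on different days" exceed the threshold without transfusion. Both definitions yield a date only if recovery happens. Section 7.0 has its own, slightly different definitions and also gives no rule for a subject who never recovers.

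For the other time-to-event endpoints the plan names an estimator: "DFS, EFS, and OS will be estimated using the method of Kaplan and Meier" (Section 11.2.3). Recovery is not in that list. Competing-risk modelling is mentioned only for geriatric assessment measures by cause of death (Section 11.1.3).

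On early death, Section 1.0 states that "The 30-day induction mortality is also high and ranges from 10-50" percent and attributes it partly to prolonged pancytopenia. Section 11.1 repeats that expected mortality "ranges from 11% for subjects 55-65 years-old with ECOG 0 to 50% for subjects older than 75 years with ECOG 2".

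**The concern.** A subject who dies in aplasia, or goes to a second induction before counts return, has no recovery date. Unless a rule supplies a value, a mean or median of observed times leaves that subject out. The missing subjects are unlikely to be a random sample: the Introduction itself links early death to prolonged low counts, so slow recoverers are the ones most at risk of having no date. The summary would then describe survivors and lean towards fast recovery.

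What is at stake is how a secondary efficacy result is described. Faster count recovery is one of the benefits that Section 3.7 reports from the study this trial sets out to confirm, so readers will look at the recovery medians.

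**Working it through.** The plan gives no sample-size, precision or expected-value figure for this endpoint, so there is nothing of its own to reproduce. The check asks how far a recoverer-only median can sit from the day by which half of all treated subjects have recovered.

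**Inputs from the document**
- 30-day induction mortality d: 10% to 50% (Section 1.0), with 30% taken as a midpoint.
- Median neutrophil recovery of 16 days, the control-group figure in Section 3.7, used only to set the scale.
- At most 21 evaluable subjects (Section 11.1).

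**Assumptions not in the document**
- Recovery time is lognormal with log-SD 0.40 (0.25 as a second value).
- Death has a constant hazard and is unrelated to recovery speed.

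**Step 1. Convert 30-day mortality to a daily hazard.** λ = −ln(1 − d)/30, giving 0.0035, 0.0119 and 0.0231 for d = 10%, 30% and 50%.

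**Step 2. Cumulative incidence of recovery.** I(t) = ∫₀ᵗ f(u)·exp(−λu) du, where f is the lognormal density. The share dying before recovery is 1 − I(∞).

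**Step 3. Two medians.** The recoverer-only median solves I(t) = I(∞)/2. The cumulative-incidence median solves I(t) = 1/2.

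| 30-day mortality | Die before recovery | Expected number of 21 | Recoverer-only median (days) | Cumulative-incidence median (days) | Gap (days) |
|---|---|---|---|---|---|
| 10% | about 6% | 21 × 0.059 = 1.2 | 15.9 | 16.4 | about 0.5 |
| 30% | about 18% | 21 × 0.184 = 3.9 | 15.5 | 17.4 | about 2 |
| 50% | about 32% | 21 × 0.321 = 6.7 | 15.1 | 19.3 | about 4 |

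Even at 10% mortality, the chance that at least one of 21 subjects has no recovery date is 1 − (1 − 0.059)²¹ = 0.72.

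**Step 4. Sensitivity to spread.** The same formulas with log-SD 0.25 give 15.9 against 16.2, 15.8 against 16.9, and 15.6 against 18.2 days: gaps of about 0.3, 1.1 and 2.5 days.

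**Step 5. Sensitivity to who dies.** Take the extreme case in which the slowest fraction p are the ones who die before recovery. The recoverer-only median is 16·exp(s·Φ⁻¹((1 − p)/2)), where s is the log-SD. For s between 0.25 and 0.40 this is 15.2-15.5 days at p = 10% and 13.7-14.5 days at p = 30%. The day by which half of all subjects have recovered stays at 16. The direction is the same as in the table.

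Re-induction without recovery would add to the subjects with no date. It is not in these figures, because the document gives no rate for it.

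**The case against.** **The plan does not say that deaths are excluded.** Correct. A reader might infer that Section 11.2.5 drops subjects who die, but the text is silent. A descriptive median could rank non-recoverers last, and their number could be tabulated. The supportable point is that handling is unspecified and that the plainest reading of the sentence gives a recoverer-only summary.

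**The mortality figures can be over-read.** It is tempting to use 10-50% directly as the share who die before recovery. Those are 30-day figures, and recovery comes around day 16 in the illustration, so many of the deaths fall later; the table makes that conversion. The 50% end belongs to subjects older than 75 with ECOG 2. The safety design also treats a true unacceptable-toxicity rate of 0.40 as grounds to stop, with probability 0.7 at stage 1. If early deaths count as treatment-related, very high mortality would often end the trial. The 10% and 30% rows are therefore the more relevant ones.

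**Unfair comparison with the earlier study.** A reader might infer that the trial's medians could not be set fairly beside its results, which "were 11 days and 14.5 days, respectively, and 16 days and 20 days in the control group". The document does not support that. Section 3.7 does not say how those medians were computed, and Section 11.2.5 plans no comparison with them. If they are recoverer-only medians, a recoverer-only summary here would be the like-for-like one.

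**Deaths are visible elsewhere.** Treatment-related mortality is part of the primary safety endpoint and OS is estimated by Kaplan-Meier. Speed of recovery among recoverers, read beside mortality, is a legitimate description. This stands, and is a reason to keep that summary with a label. It does not supply the missing rule.

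**Small numbers.** With about 19 recoverers and log-SD 0.40, the standard error of the log median is about 1.253 × 0.40/√19 = 0.115, so a 95% interval around 16 days runs from 16·exp(−1.96 × 0.115) = 12.8 to 16·exp(1.96 × 0.115) = 20.0 days. A gap of 0.5 day is small beside that; a gap of 2 to 4 days is not negligible.

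**Conclusion.** The concern holds as a gap in the specification. The plan gives a time-to-event endpoint no estimator and no rule for subjects who die or are re-induced first, in a population where it expects substantial early mortality. A plain summary of observed times would tend to look too fast, by about 0.5 day at 10% 30-day mortality, 2 days at 30% and 4 days at 50% with log-SD 0.40, and by less with a tighter spread. These sizes rest on the assumed lognormal shape, spread, 16-day scale and constant death hazard; the direction was the same in every pattern tried.

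The consequence is limited. The endpoint is secondary, single-arm and untested, and no decision rests on it, so no primary conclusion changes. The change is worth making because it is standard and cheap.

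**What to change.** In Section 11.2.5, state that in all treated subjects the cumulative incidence of neutrophil and of platelet recovery will be estimated separately for each course, with death or the next anti-leukemic therapy without recovery as competing events. Take the median from that curve, or report it as not reached. Give the number who never recover and why. Any recoverer-only median can stay as a labelled supplementary summary. Censoring deaths in a Kaplan-Meier curve would not fully solve the problem, because it treats the dead as if they could still recover.

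State one time origin. Section 11.2.5 defines a time as a date and gives no starting point, while Section 6.2.3 calls the infusion day day 0. Some courses have no infusion, so the first day of chemotherapy is an origin that exists for every course. Reconcile the recovery definitions in Sections 7.0 and 11.2.5 in the same edit.

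The cost is a little analysis work, and recovery may look slightly slower. For induction, the daily blood counts and survival follow-up are already planned. After consolidation, Section 6.4.2 allows counts every two weeks, so recovery dates there may be coarse, and the report should say so.

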12.0 ANTICIPATED TOXICITY OF DLI PROCEDURE

12.1 GVHD

Although GVHD is a common complication of DLI, given the absence of GVHD in a similar study by Guo et al.[6], we do not anticipate any GVHD in our study. This is because unlike a traditional transplant in which that patient engrafts with donor cells, which then go on to cause GVHD, we do not expect long-term engraftment, and therefore donor cells should not persist long enough to cause GVHD.

12.2 Infections

Although infections are a common complication of hematopoietic stem cell transplantation and donor lymphocyte infusion, we do not expect any of the procedures specifically associated with DLI to increase the risk of infection beyond that associated with induction and consolidation chemotherapy.

12.3 Infusion Reaction/Engraftment Syndrome

Patients may experience reactions to the infusion itself including fever, chills, skin rash, pulmonary infiltrates, diarrhea, hepatic dysfunction, renal dysfunction, or confusion. Any such reaction would be transient and we would respond by slowing the infusion as per 6.3.4. Steroids, tocilizumab, acetaminophen, and intravenous fluids may also be administered in the case of such a reaction.

12.4 Risk of sensitization

Infusion of haploididentical cells may result in alloimmunization of the donor; i.e., sensitization, which may make engraftment after allogeneic hematopoietic stem cell transplantation more difficult, if such a therapy were planned later. However, as an institution, we have considerable experience overcoming sensitization and alloimmunization in the allogeneic transplant situation, and we do not anticipate significant problems with engraftment should an allogeneic transplantation be needed in the future.

13.0 DRUG INFORMATION

13.1 Cytarabine (ara-C)

13.1.1 Source and Pharmacology: Cytarabine for Injection USP, commonly known as ara-C, an antineoplastic for intravenous, intrathecal, or subcutaneous administration, contains sterile lyophilized cytarabine (1- β -D-Arabinofuranosylcytosine). Cytarabine is an odorless, white to off-white, crystalline powder which is freely soluble in water and slightly soluble in alcohol and in chloroform. Cytarabine is a synthetic nucleoside which differs from the normal nucleosides cytidine and deoxycytidine in that the sugar moiety is arabinose rather than ribose or deoxyribose.

13.1.2 Formulation and Stability: Cytarabine is rapidly metabolized and is not effective when taken orally; less than 20% of the orally administered dose is absorbed from the gastrointestinal tract. Following rapid intravenous injection of cytarabine labeled with tritium, the disappearance from plasma is biphasic. There is an initial distributive phase with a half-life of about 10 minutes, followed by a second elimination phase with a half-life of about 1 to 3 hours. After the distributive phase, more than 80% of plasma radioactivity can be accounted for by the inactive metabolite 1- β -D-Arabinofuranosyluracil (ara-U). Within 24 hours, about 80% of the administered radioactivity can be recovered in the urine, approximately 90% of which is excreted as ara-U. Relatively constant plasma levels can be achieved by continuous intravenous infusion. After subcutaneous or intramuscular administration of cytarabine labeled with tritium, peak plasma levels of radioactivity are achieved about 20 to 60 minutes after injection and are considerably lower than those after intravenous administration.

13.1.3 Supplier: Commercial Supply.

13.1.4 Toxicity: Because cytarabine is a bone marrow suppressant, anemia, leukopenia, thrombocytopenia, megaloblastosis, and reduced reticulocytes can be expected as a result of administration of cytarabine. The severity of these reactions are dose and schedule dependent. Cellular changes in the morphology of bone marrow and peripheral smears can be expected. Following 5-day constant infusions or acute injections of 50 to 600 mg/m², white cell depression follows a biphasic course. Regardless of initial count, dosage level, or schedule, there is an initial fall starting the first 24 hours with a nadir at days 7 to 9. Viral, bacterial, fungal, parasitic, or saprophytic infections, in any location in the body may be associated with the use of cytarabine alone or in combination with other immunosuppressive agents following immunosuppressant doses that affect cellular or humoral immunity. These infections may be mild, but can be severe and at times fatal.

13.1.5 Route of Administration: IV over 5 to 7 days.

13.2 Idarubicin

13.2.1 Source and Pharmacology: Idarubicin HCl Injection contains idarubicin hydrochloride and is a sterile, semi-synthetic, preservative-free solution antineoplastic anthracycline for intravenous use.

Idarubicin HCl is a DNA-intercalating analog of daunorubicin which has an inhibitory effect on nucleic acid synthesis and interacts with the enzyme topoisomerase II. The absence of a methoxy group at position 4 of the anthracycline structure gives the compound a high lipophilicity which results in an increased rate of cellular uptake compared with other anthracyclines.

13.2.2 Formulation and Stability: Idarubicin HCl Injection is a sterile, red-orange, isotonic parenteral preservative-free solution, available in 5 mL (5 mg), 10 mL (10mg) and 20 mL (20 mg) single-use-only vials. Each mL contains idarubicin HCl 1 mg and the following inactive ingredients: glycerin 25 mg and water for injection q.s. Hydrochloric acid is used to adjust the pH to a target of 3.5.

Pharmacokinetic studies have been performed in adult leukemia patients with normal renal and hepatic function following intravenous administration of 10 to 12 mg/m² of idarubicin daily for 3 to 4 days as a single agent or combined with cytarabine. The plasma concentrations of idarubicin are best described by a two or three compartment open model. The elimination rate of idarubicin from plasma is slow with an estimated mean terminal half-life of 22 hours (range, 4 to 48 hours) when used as a single agent and 20 hours (range, 7 to 38 hours) when used in combination with cytarabine. The elimination of the primary active metabolite, idarubicinol, is considerably slower than that of the parent drug with an estimated mean terminal half-life that exceeds 45

Chemo with Adoptive Haplo DLI

hours; hence, its plasma levels are sustained for a period greater than 8 days.

13.2.3 Supplier: Commercial Supply.

13.2.4 Toxicity: Idarubicin is intended for administration under the supervision of a physician who is experienced in leukemia chemotherapy. Idarubicin is a potent bone marrow suppressant. Idarubicin should not be given to patients with pre-existing bone marrow suppression induced by previous drug therapy or radiotherapy unless the benefit warrants the risk.

Severe myelosuppression will occur in all patients given a therapeutic dose of this agent for induction, consolidation or maintenance. Careful hematologic monitoring is required. Deaths due to infection and/or bleeding have been reported during the period of severe myelosuppression. Facilities with laboratory and supportive resources adequate to monitor drug tolerability and protect and maintain a patient compromised by drug toxicity should be available. It must be possible to treat rapidly and completely a severe hemorrhagic condition and/or a severe infection.

Pre-existing heart disease and previous therapy with anthracyclines at high cumulative doses or other potentially cardiotoxic agents are co-factors for increased risk of idarubicin-induced cardiac toxicity and the benefit to risk ratio of idarubicin therapy in such patients should be weighed before starting treatment with idarubicin. Myocardial toxicity as manifested by potentially fatal congestive heart failure, acute life-threatening arrhythmias or other cardiomyopathies may occur following therapy with idarubicin. Appropriate therapeutic measures for the management of congestive heart failure and/or arrhythmias are indicated.

Cardiac function should be carefully monitored during treatment in order to minimize the risk of cardiac toxicity of the type described for other anthracycline compounds. The risk of such myocardial toxicity may be higher following concomitant or previous radiation to the mediastinal-pericardial area or in patients with anemia, bone marrow depression, infections, leukemic pericarditis and/or myocarditis. While there are no reliable means for predicting congestive heart failure, cardiomyopathy induced by anthracyclines is usually associated with a decrease of the left ventricular ejection fraction (LVEF) from pretreatment baseline values. Since hepatic and/or renal function impairment can affect the disposition of idarubicin, liver and kidney function should be evaluated with

Chemo with Adoptive Haplo DLI

conventional clinical laboratory tests (using serum bilirubin and serum creatinine as indicators) prior to and during treatment. In a number of Phase III clinical trials, treatment was not given if bilirubin and/or creatinine serum levels exceeded 2 mg%. However, in one Phase III trial, patients with bilirubin levels between 2.6 and 5 mg% received the anthracycline with a 50% reduction in dose. Dose reduction of idarubicin should be considered if the bilirubin and/or creatinine levels are above the normal range.

